12.6 Progression-Free Survival

Progression free survival is defined as the duration of time from start of treatment to time of progression or death, whichever occurs first.

12.7 Response Review

Not applicable.

12.8 Unblinding Procedures

Not applicable.

12.9 Stopping Rules

Adverse event stopping rule: Accrual will be temporarily suspended to this study if (a) at any time, 2 patients have experienced a grade 5 event considered at least possibly related to the study treatment and not related to disease progression or (b) more than 40% of all patients, when accrual is equal to or greater than 10 patients, have experienced a grade 3 or higher adverse event. In addition, each grade 5 event will be reviewed at the time of occurrence to determine whether study accrual should be suspended to protect the safety of patients. This adverse event stopping rule may be altered in the event of the study reopening after a temporary suspension or should new information become available related to the safety of the study drug.

13. CORRELATIVE STUDIES

13.1 Tissue procurement and Handling

The first 10 patients who are enrolled and initiate treatment will undergo paired pre-treatment and on-treatment tissue biopsies. The baseline biopsy specimen will be obtained within 21 days of cycle 1 day 1, provided consent is obtained and the other eligibility criteria are met. The on-treatment biopsy specimen will be obtained on cycle 1, days 1 or 2.

The same tumor lesion should be biopsied at both time points whenever possible. Specimens are obtained using a 16-18 gauge core needle under imaging guidance by an interventional radiologist at the treating institution. At least 4 cores are obtained, and up to 6-8 cores if feasible (with safety of the procedure prioritized in all cases). The first 4 cores are placed in FFPE and the subsequent 2-4 cores are cryopreserved and flash frozen. From the FFPE material, an H&E section should be cut for confirmation/diagnostic purposes, to be reviewed at the institution collecting the sample as per standard of care. These following specifications apply:

- (1) A 16 to 18 gauge needle is satisfactory;
- (2) Time from core needle biopsy (CNB) removal to initiation of fixation should be \leq 30 min;
- (3) CNB material should be immersed in sufficient volume of 10% neutral buffered formalin to

ensure adequate fixation (\geq 15 to 20 times greater than estimated volume of CNB);

(4) Formalin fixation to last between 6-72 hours at room temperature; and after fixation, proceed to paraffin embedding. Tissue blocks should be stored at ambient conditions.

(5) Material should be labeled, accessioned and stored consistent with standard of care policies and procedures at the participating institution.

The tissue will be used for correlative studies evaluating ATX-101's effects on the immune microenvironment, intracellular signaling pathways and DNA damage response pathways.

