2.3 Correlative Science Objectives

2.3.1 To evaluate the mechanistic effects of ATX-101 in LMS and dedifferentiated LPS by evaluating ATX-101's effects on the immune microenvironment, intracellular signaling pathways and DNA damage response using paired tumor biopsies from a subset of 10 patients, and to use the results of these analyses to identify candidate biomarkers for sensitivity and resistance to ATX-101 in the sarcoma population.

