4. STUDY DESIGN

4.1 General Design

[figure not shown]
This is a phase II, single-arm, open-label, Simon 2-stage study evaluating the efficacy of ATX-101 in patients with unresectable or metastatic LMS or dedifferentiated LPS who have received treatment with at least one prior systemic therapy.

Because clinical data with ATX-101 is limited, a safety lead-in will be conducted among the first 10 patients enrolled and treated on the study. The safety lead-in is described in Section 4.2.

The study will be conducted at Columbia University Irving Medical Center. All subjects will be treated with the same agent and dose, ATX-101, at 60 mg/m² IV weekly in continuous 21 day cycles. Patients will receive treatment at the discretion of the principal investigator until disease progression, unacceptable toxicity or adverse event(s) or withdrawal of consent.

The primary endpoint is the progression free rate at 12 weeks (PFR₁₂). Secondary endpoints include overall survival, progression free survival, overall response rate and safety profile.

For further details on the statistical design, see Section 9.

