5.1 Inclusion Criteria

	(LMS). Pathology review occurs at the	center enrolling the patient on this trial.		
5.1.2	Disease must be locally advanced and unresectable or metastatic. Disease which may be resected but with an associated level of morbidity deemed unacceptable by the treating clinician is considered eligible.			
5.1.3	Patients must have measurable disease by RECIST criteria version 1.1. In addition, the first 10 patients enrolled on the study must have a site of disease amenable to image-guided biopsy at minimal risk or less, and must agree to undergo this biopsy.			
5.1.4	within the 12 weeks prior to study enro enrolling the patient on the study.	ression, either clinically or radiographically, llment, as determined by the investigator		
5.1.5	Patients must have been treated with at least one prior systemic regimen for advanced sarcoma: LMS: Anthracycline-based chemotherapy, or gemcitabine/docetaxel. LPS: No specification as to the prior treatment received. Neoadjuvant or adjuvant systemic therapy does not qualify as prior treatment			
5.1.6	unless completed within 6 months of disease relapse.Patients must be age 18 years or older. Because the safety of ATX-101 in patientsless than 18 years of age has not been characterized, children are excluded from thepresent study.			
5.1.7	Patients must demonstrate an ECOG pe	erformance status of 0-2.		
5.1.8	Patients must demonstrate normal organ and marrow function as defined below:			
	Absolute neutrophil count (ANC) Platelet count Creatinine Calculated creatinine clearance Total bilirubin AST/ALT	 ≥ 1,500/mm³ ≥ 100,000/mm³ ≤ 1.5 times upper limit of normal OR > 45 mL/min* ≤ 1.5 times upper limit of normal** ≤ 1.5 times upper limit of normal** 		
	Notes:Upper limit of normal is defined by the clinical laboratory performing the test.* Using the lean body mass formula only (Modified Cockcroft Gault)** If transaminase elevation and/or bilirubin elevation is attributed to the presenceof liver metastases, a total bilirubin ≤ 2.5 times the upper limit of normal and anAST and ALT ≤ 2.5 times the upper limit of normal are permissible. Patients withan elevated bilirubin level that is attributed to an inherited disorder, such asGilbert's disease, may be enrolled at the discretion of the principal investigator.			

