11. STUDY CALENDAR

CBC w/differential (1,3)*	Х	Х	Х	Х	Х		Х		Х
Comprehensive metabolic panel (1,3,4)*	Х	Х	Х	Х	Х		Х		Х
Serum or urine pregnancy test (1, 3)	Х								Х
Urinalysis (1, 3)	Х						Х		Х
CT or MRI of chest, abdomen, pelvis (2)	Х						Х		Х
Tumor biopsy for correlative studies (5)	Х				X				
Follow-up telephone contact (6)	llow-up telephone contact (6)				Х				
*Clinical/laboratory safety assessm	ents must	be con	nple	ted w	ithin 24	4 hours	prior to	treatmen	t.

(1) Screening procedures must be completed within 21 days of initiating study treatment, with the exception of the serum or urine pregnancy test, which must be completed within 7 days of initiating study treatment. Protocol-specified screening procedures that are performed as part of standard of care and are within the specified timeframes may be used for screening purposes.

(2) Baseline imaging can include either (a) CT, spiral CT or MRI, or (b) FDG-PET with diagnostic CT performed with IV and oral contrast and CT acquired with 5 mm or less slice thickness. Imaging studies used for baseline tumor measurements must be performed within 21 days of initiating study treatment. Imaging studies are performed every 2 cycles (6 weeks, 42 days) for the first 36 weeks of study treatment, and then every 3 cycles (9 weeks, 63 days) thereafter. Imaging studies may be performed +/- 5 days from the required date. In the event of dose delays/holds, imaging studies should still be obtained at the scheduled timepoints as measured from cycle 1 day 1, without delays to account for dose delays/holds. Confirmatory scans must be obtained at least 4 weeks after the documentation of an objective response. It is acceptable to perform confirmatory assessments at the next appointed evaluation per protocol. Response assessment should include assessment of all sites of disease and use the same imaging method as used at baseline whenever possible.

(3) All laboratory studies may be performed +/- 3 days from the required date. Local laboratory testing is permitted, except for the serum/urine pregnancy test.

(4) Comprehensive metabolic panel includes albumin, alkaline phosphatase, total bilirubin, bicarbonate, blood urea nitrogen, calcium, chloride, creatinine, glucose, potassium, total protein, AST, ALT and sodium.

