(5) The first 10 patients enrolled on the study will undergo paired pre-treatment and on-treatment biopsies. The baseline biopsy specimen must be obtained within 21 days of cycle 1 day 1, provided consent is obtained and other eligibility criteria are met. The on-treatment biopsy specimen will be performed cycle 2, days 1 or 2. Biopsies will be obtained from the same anatomic site of disease whenever possible.

(6) A post-study follow-up contact via telephone by research staff will be conducted every 3 months during the first year after the end of study participation, and then every 6 months thereafter. Information is obtained on disease status, survival status, and new anti-cancer therapy received. Follow-up continues for at least 3 years as measured from the date of study registration or until death, whichever comes first.

(7) The end-of-study visit must be scheduled within 28 days after the last dose of study drug (+/-7 days) and before starting any new anti-neoplastic therapy.

(8) Clinical assessments will occur on days 1, 8 and 15 of cycle 1, and then on day 1 of all cycles thereafter. Clinical assessments may occur +/- 3 days from the planned date but must occur within 24 hours of ATX-101 administration.

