15.5 Analysis of Correlative Science Endpoints

Analysis of correlative endpoints will be considered exploratory and hypothesis generating.

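### Section 13.1 puts the on-treatment biopsy in cycle 1, the study calendar puts it in cycle 2; Section 13.1 is probably the slip and could yield a second pre-dose sample

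*Combined protocol and SAP*

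**What the plan says.** Section 2.3.1 sets a correlative objective that relies on "paired tumor biopsies from a subset of 10 patients". It covers the immune microenvironment, intracellular signaling, the DNA damage response and candidate biomarkers, and gives no biopsy dates. Under Section 5.1.3 the first 10 patients "must have a site of disease amenable to image-guided biopsy at minimal risk or less, and must agree to undergo this biopsy", so for them the biopsy is a condition of entry.

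The timing appears in two places:

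- Section 13.1, baseline: "The baseline biopsy specimen will be obtained within 21 days of cycle 1 day 1". On treatment: "The on-treatment biopsy specimen will be obtained on cycle 1, days 1 or 2".
- Section 11, footnote 5, gives the same 21-day baseline window. On treatment: "The on-treatment biopsy specimen will be performed cycle 2, days 1 or 2".

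The biopsy row of the Section 11 grid has a mark at screening, three empty cells, and then a second mark. Neither section says whether the on-treatment sample is taken before or after that day's infusion. Section 15.5 limits the weight of the results: "Analysis of correlative endpoints will be considered exploratory and hypothesis generating".

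**The concern.** Both statements are current instructions for one procedure in one set of patients, and they cannot both be followed. The issue is the contradiction, not the merit of either time point.

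Section 13.1 is where staff would look for how to obtain the tissue. Followed literally, it allows a biopsy on the day of the first infusion without saying that the infusion comes first. A patient could then have two untreated samples, and such a pair cannot show a drug effect. Otherwise the sample follows a single dose instead of about three weeks of treatment. If some patients were sampled by one section and some by the other, the pairs would not be comparable, and there are only 10.

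The ambiguity applies from the first patient enrolled. A mistimed sample cannot be recovered without another image-guided core biopsy, which Section 13.1 sets at a minimum of 4 cores. Whichever text is followed, the other is breached, and Section 14.3 sends protocol deviations to the DSMC and then to the IRB.

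**Working it through.** No power, alpha or sample size figure is involved. The check is a comparison of the texts and a count of doses.

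**Inputs**

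- Dosing (Section 4.1): "IV weekly in continuous 21 day cycles". The calendar places infusions on days 1, 8 and 15 of each cycle.
- Biopsy dates: Section 13.1 and footnote 5 of Section 11, as quoted above.
- Assumption: no dose delays, and visit windows ignored.

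**Study days**

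Study day = 21 × (cycle − 1) + day of cycle.

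- Section 13.1: 21 × 0 + 1 = day 1, or 21 × 0 + 2 = day 2.
- Calendar: 21 × 1 + 1 = day 22, or 21 × 1 + 2 = day 23.
- Difference: 22 − 1 = 21 days.

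**Doses received before the sample** (infusions on study days 1, 8, 15 and 22)

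| Source | Sample taken | Doses before sample |
|---|---|---|
| 13.1 | Cycle 1 day 1, before infusion | 0 |
| 13.1 | Cycle 1 day 1, after infusion | 1 |
| 13.1 | Cycle 1 day 2 | 1 |
| Calendar | Cycle 2 day 1, before infusion | 3 |
| Calendar | Cycle 2 day 1, after infusion | 4 |
| Calendar | Cycle 2 day 2 | 4 |

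Like for like, the gap is three doses (3 − 0, or 4 − 1).

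**Which text is the likelier error**

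1. The grid is broken in the extracted text, so its alignment has to be inferred from other rows. The blood count row has five consecutive marks, which fit screening, cycle 1 days 1, 8 and 15, and cycle 2 day 1. The imaging row's first mark after screening falls two cells further on, which fits cycle 3 day 1 and the 6-week imaging interval in footnote 2. On that alignment the second biopsy mark is the fifth cell, cycle 2 day 1, and cycle 1 has no mark.
2. Section 13.1 itself calls the specimen on-treatment. A date that can precede the first dose fits that label poorly; cycle 2, days 1 or 2 fits it without qualification.

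Both points favor the calendar. Nothing in the protocol settles it.

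**The case against.** The strongest objection concerns direction. Section 3.1.1 reports a half-life of a few minutes in human blood in vitro and rapid tissue uptake in rats. A sample shortly after the first infusion is therefore a conceivable pharmacodynamic time point for signaling or DNA damage response. The objective names no time, and the grid row cites footnote 5, so grid and footnote are not fully independent evidence. This stands as a limit on certainty about which text is wrong. It does not remove the contradiction: the protocol never offers that rationale, and if an early sample were intended, the calendar would need correcting instead.

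Second, the pre-dose sample is the least likely outcome, because it would contradict the specimen's own label, and a day 2 sample follows a dose under the planned schedule. That is fair. It is a possibility the wording leaves open, and a one-dose sample is the more realistic result.

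Third, the practical risk is modest. This is a single-center study with visits laid out in the calendar, staff may well notice the conflict, the number of biopsies is the same either way, and the analyses are exploratory. All of this limits the severity. It gives no reason to leave two incompatible instructions in place.

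**Conclusion.** The concern holds. Sections 13.1 and 11 give incompatible dates for the same biopsy, 21 days and three scheduled doses apart, affecting up to 10 patients. Confidence is high that the contradiction exists. That Section 13.1 is the erroneous one is probable, resting on footnote 5, the inferred grid alignment and the on-treatment label. The dose counts assume no delays.

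The reach is limited to the exploratory correlative objective. No statistical test is specified for these endpoints, so no effect on power or type 1 error is claimed, and the primary endpoint, Simon design, sample size and lead-in rules are untouched. The correction should be made because the tissue is scarce, the biopsy is required for entry, and the error would apply from the first patient.

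**What to change.** Have the investigator confirm the intended time point. Unless an early sample was meant, change the on-treatment biopsy in Section 13.1 to cycle 2, days 1 or 2, matching the grid and footnote 5 of Section 11. If an early sample was meant, correct the calendar instead. It would also help, though it is not part of the contradiction, to state in both places whether the sample is taken before or after that day's infusion, since this alone moves a day 1 sample by one dose.

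The cost is one line of text, with no added biopsy, patient or expense.

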14. DATA REPORTING / REGULATORY REQUIREMENTS

Adverse event lists, guidelines, and instructions for reporting can be found in Section 10 (Adverse Events: List and Reporting Requirements). The Data Safety Monitoring Plan is described in Section 12.2.

14.1 Data Collection

The Herbert Irving Comprehensive Cancer Center has an electronic clinical trials and data management system (CTMS) that will be used for data collection. CRFs for the study will be built into the CTMS for data entry. The system has full auditing capabilities which is web-based and housed on a server in a fully HIPAA compliant server room with restricted access and video camera monitoring. All users must login with their own application username and password. Users off campus must first access the Virtual Private Network with their assigned campus username and password and then use their application credentials. Users are only able to see study information if they are indicated as study personnel in our electronic IRB system. Users are limited to access based on the role assigned in their corresponding protocol. Subject data is entered directly into the system, which (in the case of Columbia subjects) confirms the correct identity of patients via an interface with the electronic medical patient index. Staff with the appropriate IRB defined roles can run reports within the system for reporting purposes.

14.2 Data Reporting

Case Report Forms will be completed for each subject enrolled into the clinical study through the CTMS. It is the investigator's responsibility for ensuring that all clinical and laboratory data entered on the corresponding CRFs are complete, accurate and authentic.

14.3 Data and Safety Monitoring Committee

The NCI-approved Data Safety and Monitoring Committee (DSMC) of the Herbert Irving Comprehensive Cancer Center (HICCC) will monitor every subject who receives treatment on this protocol for toxicity. This protocol will adhere to the policies of the currently approved HICCC Data and Safety Monitoring Plan (DSMP), which is in accordance with NCI and CUMC-IRB policy and guidelines. The committee is chair is appointed by the HICCC Director. The committee consists of HICCC faculty and staff with expertise in oncology, research pharmacy, research nursing, and data management. The DSMC convenes twice a month to review patient safety and the conduct of the trial. The PI will submit data and safety monitoring reports to the DSMC at a frequency to be determined by the DSMC based on risk to the subjects.

At the time of renewal, the study team will submit the most recent DSMC approval letter for safety review to the CUMC IRB. Any modifications that are required by the DSMC to ensure patient safety will be submitted to the IRB. All protocol deviations, violations, and eligibility waivers will be submitted to and approved by the DSMC prior to being reported to the IRB. All study data reviewed and discussed during these meetings will be kept confidential.

For multicenter research, the principal investigator will assure that there is a mechanism in place to distribute the report to all participating investigators for submission to their local IRB. The report will document that a review of data and outcomes across all centers took place on a given date. It will summarize the DSMC's review of the cumulative toxicities reported from all participating sites without specific disclosure by treatment arm. It will also inform site investigators of the study the DSMC's conclusion with respect to progress or need for modification of the protocol.

14.4 Quality Control and Quality Assurance

Independent monitoring of the clinical study for protocol and GCP compliance will be conducted periodically by the CPDM Compliance Core on behalf of the HICCC DSMC. Additionally, the Compliance Oversight Committee of the IRB at Columbia University Medical Center may audit the study at any time per institutional policies and procedures. The investigator-sponsor and Columbia University Medical Center will permit direct access of the study monitors and appropriate regulatory authorities to the study data and to the corresponding source data and documents to verify the accuracy of this data.

A risk-based approach will be used by the Compliance Core to determine the frequency, number of subject charts, and data elements to be monitored. The Compliance Coordinator will review the study status and summarize enrollment, toxicities, SAEs/UPs, dose escalation, statistical endpoints (e.g., stopping rules), etc. for the full DSMC membership at the regularly scheduled meetings.

Internal On-site Monitoring:

- Initial, recurrent, and close-out on-site monitoring visits will also be conducted at remote clinical sites, as appropriate/feasible. Other sites will have monitoring performed remotely (see below for further details).
- The study Monitoring Visit Log will be completed and signed by the monitor and the PI/CRNP/CRN and/or CRC and will be filed in the regulatory binder.
- The Compliance Coordinator will communicate with the site coordinator/Site Principle Investigator to schedule the monitoring visit and arrange for access to study materials and documentation.
- The assigned Compliance Coordinator will monitor IIT trials within 1 month after

the first subject is enrolled and throughout the life of the study to ensure that the study is being conducted in accordance with the protocol, GCP, applicable federal and local regulations, and per all applicable SOPs. The Compliance Coordinator is responsible to notify the PI and CRNP/CRN/CRC of upcoming monitor visits and convey what information and documentation will be required for the visit(s). The Compliance Coordinator is responsible for verifying that informed consent is properly obtained, eligibility is met (via the central registration process), and all study procedures are conducted according to the study protocol. The Compliance Coordinator will also verify that the data reported in the CRF's accurately reflect source documents, that all toxicities have been reported to date, and that all SAE's/UPs/deviations/violations have been reported according to local IRB and HICCC DSMC requirements. The Compliance Coordinator will issue queries and ensure resolution in a timely and efficient manner. The Compliance Coordinator will also monitor for applicable regulatory compliance and research pharmacy compliance (if applicable) and communicate any deficiencies as appropriate.

